3.6. Missing Data and Outliers

3.6.1. Missing Data

In general, missing data will not be imputed unless methods for handling missing data are specified. Exceptions are presented in this document.

For missing last dosing date of study drug, imputation rules are described in Section 4.2. The handling of missing or incomplete dates for AE onset is described in Section 7.1.6.4, and for prior HBV and concomitant medications in Section 7.4.

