Table 3-10. Cohort 1, Cohort 2 Groups A and B: Analysis Visit Windows for Posttreatment Hematology, Chemistry, Coagulation, Quantitative Plasma HBV DNA, HBV genotyping, Quantitative HBV Serology (HBsAg, HBcrAg, HBeAg, and HBV RNA), Qualitative HBV Serology (HBeAg, HBeAb, HBsAg, and HBsAb) and Vital Signs

		Visit Window FU Day	
Visit	FU Day	Lower Limit	Upper Limit
FU Week 2*	15	4	22
FU Week 4	29	23	43
FU Week 8	57	44	71
FU Week 12	85	72	127
FU Week 24	169	128	211
FU Week 36	253	212	295
FU Week 48	337	296	≥ 337

^{*} FU Week 2 was defined in protocol amendment 1, but was removed from protocol amendment 2. Since a substantial amount of participants have already completed FU Week 2 per protocol amendment 1, this visit will be kept in analysis.

Table 3-11. Cohort 2 Groups A and B: Analysis Visit Windows for Posttreatment APRI and FibroTest

		Visit Window FU Day	
Visit	FU Day	Lower Limit	Upper Limit
FU Week 12	85	4	211
FU Week 48	337	212	≥ 337

Table 3-12. Cohort 1, Cohort 2 Groups A and B: Analysis Visit Windows for Posttreatment Body Weight, ECG, Estimated Creatinine Clearance (using the Cockcroft-Gault method)

		Visit Window FU Day	
Visit	FU Day	Lower Limit	Upper Limit
FU Week 48	337	4	≥ 337

3.8.3. Selection of Data in the Event of Multiple Records in an Analysis Visit Window

Depending on the statistical analysis method, single values may be required for each analysis window. For example, change from baseline by visit usually requires a single value, whereas a time-to-event analysis would not require 1 value per analysis window.

If multiple valid, nonmissing, continuous measurements exist in an analysis window, records will be chosen based on the following rules if a single value is needed:

- For baseline, the last nonmissing value on or prior to the first dosing date of study drug will be selected, unless specified differently. If multiple measurements occur on the same day, the last nonmissing value prior to the time of first dosing of study drug will be considered as the baseline value. If there are multiple records with the same time or no time recorded on the same day, the baseline value will be the average of these measurements.
- For postbaseline values (except for alanine aminotransferase [ALT]):
 - The record closest to the nominal day for that visit will be selected.
 - If there are 2 records that are equidistant from the nominal day, the later record will be selected.

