6.2.2. Analysis Methods for Secondary Efficacy Endpoints

The secondary efficacy analyses will be performed on FAS.

- The proportions of participants with HBsAg loss with and without anti-HBsAg seroconversion will be summarized by cohort and visit.
- The proportion of participants with HBeAg loss with and without anti-HBeAg seroconversion will be summarized by cohort and visit for participants who are HBeAg positive at baseline.
- The proportion of participants who remain off NUC treatment during FU will be summarized by cohort and FU visit.

Data collected on Visit Date CRF will be used to identify participants who entered FU phase. If a participant had any follow-up visit with nonmissing visit date, then this participant will be considered as entered FU phase.

For participants who entered the FU phase, if NUC treatment was ended no later than FU Week 1 visit, and there is no NUC treatment re-initiation during the FU phase, then this participant is considered as remaining off NUC treatment during FU phase. If partial start/stop dates are entered, any NUC treatment with the month and year (if day is missing) or year (if day and month are missing) of either start or stop date after FU Week 1 will be considered as using NUC treatments. Participants with completely missing NUC treatment start and stop dates will be considered as using NUC treatments, unless otherwise specified.

A list of NUC treatments can be found in Appendix 3.

• The proportion of participants experiencing HBV virologic breakthrough during study treatment(s) will be summarized by cohort.

The HBV virologic breakthrough is defined as confirmed HBV DNA ≥ LLOQ after 2 consecutive HBV DNA < LLOQ in participants who are complying with NUC therapy OR confirmed HBV DNA ≥ 1 log10 IU/mL increase from nadir during study treatments.

In addition, a summary table will be provided for HBsAg-related serology results. The proportion of participants who have ever had HBsAg loss, confirmed HBsAg loss, on-treatment HBsAg loss, posttreatment HBsAg loss (for participants with positive HBsAg at the end of the on-treatment period), HBsAg loss with HBsAb seroconversion, HBsAg loss with HBsAb seroconversion will be summarized.

For all the above summaries, within Cohort 2, the summary will be presented by treatment group (Group A or Group B) and HBsAg category (HBsAg > 3 and $\le 3 \log 10 \text{ IU/mL}$).

HBV serology definitions:

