- **HBsAg loss**: HBsAg changing from positive at baseline to negative at any postbaseline visit.
- Confirmed HBsAg loss: HBsAg loss confirmed by any 2 consecutive results.
- HBsAg loss reversion: Any postbaseline HBsAg positive result following HBsAg loss.
- **HBsAb seroconversion**: HBsAb changing from negative or missing at baseline to positive at any postbaseline visit.
- Confirmed HBsAb seroconversion: HBsAb changing from negative or missing at baseline to positive at any postbaseline visit confirmed by any 2 consecutive results.
- **HBsAb** seroreversion: Any postbaseline HBsAb negative result following HBsAb seroconversion.

Both baseline and postbaseline borderline results for HBeAg, HBeAb, HBsAg, and HBsAb will be imputed as follows:

- HBsAb/HBeAb borderline/equivocal → HBsAb/HBeAb negative
- HBsAg/HBeAg borderline/equivocal → HBsAg/HBeAg positive

Missing data will be treated as a nonevent unless otherwise specified (eg, no HBsAg loss, no seroconversion, etc.)

HBeAg-related terminology is defined similarly.

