Sparse PK for VIR-2218 ⁿ		X			X				X													
Sparse PK for SLGN ⁿ					X				X			X										
Estimated creatinine clearance (using the Cockcroft-Gault method)	X	X			Х								Х	X								Х
Urinalysis	X	X	X	X	X			X	X	X	X	X	X	X								
Urine Drug and Alcohol Screen	X																					
Autoantibodies	X																					
TSH	X									X			X	X								
FSH ^o	X																					
Serum Pregnancy TestP	X													Х								
Urine Pregnancy Test ^p		Х	Х	Х	Х			Х	Х	X	X	X	X			X	Хр	Х	Хр	X	X	Х
Enrollment		X																				
Dispense and Administer TAF as appropriate						7	Tenofo	vir ala	fenam	ide (T	TAF) 2	25-mg t	ablet adminis	stered or	ally da	ly for u	p to 84	weeks				

	Screening	Baseline		,	Treat	ment (Cycles	Wee	ek (± 2	2 days	s) a		EOT (-5 days)				F	ollow-ı	ıp Weel	ks ^b		
	(45 days)	Day 1	4	8	12	13 ^c	14	16	20	24	28	32	36/EOT	EDd	1¢	4	8c	12	16 ^c	24	36	48
Dispense & Administer VIR-2218 SC as appropriate		X	X	X	X			X	X													
Dispense & Administer SLGN9 as appropriate					X	X	Х	Х	X	X	X	X										
Study Drug Accountability			X	X	X		X	X	X	X	X	X	X									

AE = adverse event; APRI = AST to Platelet Ratio Index; CT = computed tomography; ddPCR = digital droplet polymerase chain reaction; ECG = electrocardiogram; ED = early discontinuation; EOT = end of treatment; FSH = follicle-stimulating hormone; FU = follow-up; HBcAg = hepatitis B core-related antigen; HBeAb = hepatitis B e antibody; HBeAg = hepatitis B e antigen; HBv = hepatitis B virus; HCC = hepatocellular carcinoma; HCV = hepatitis C virus; HDV = hepatitis D virus;

IV = intravenous; PBMC = peripheral blood mononuclear cells; PK = pharmacokinetic; SAE = serious adverse event; SC = subcutaneous; SLGN = selgantolimod; TAF = tenofovir alafenamide;

TSH = thyroid-stimulating hormone

- a All study visits except for Weeks 13 and 14.
- b FU Week 1 will have a visit window of + 3 days, FU Weeks 4 through FU Week 16 will have a visit window of ± 5 days, and FU Weeks 24 through FU Week 48 will have a visit window of ± 14 days.
- c Week 13, FU Week 8, and FU Week 16 will be conducted as a virtual/telephonic visit to review AEs, concomitant medications, and overall health of the participant by investigator.
- d The ED visit should be performed within 14 days from notification of study discontinuation. If ED is done in FU period, all of these procedures should be performed.

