Estimated creatinine clearance (using the Cockcroft-Gault method)	X	х					X								X	Х								Х
Urinalysis	X	X			X	X	X			X	X	X	X	X	X	X								
Urine Drug and Alcohol Screen	X																							
Autoantibodies	X																							
TSH	X						X (Cohort 2 Group B)					Х			X	X								
FSH ^q	X																							

					7	Treatment (Cycles Week	x (± 2 d	lays)ª						EOT (-5 days)				Foll	ow-u	p Wee	eks ^b		_
				Cohort 2 Group B only								ı	Cohor	t 2 only	(Cohort 2 Group B)									
	Screening (45 days)	BL Day 1	1°	2 ^d	4	8	12	13°	14	16	20	24	28	32	/ 36 (Cohort 2 Group A)	EDe	1 ^{b,c}	4	8c	12	16	24	36	48
Serum Pregnancy Test ^r	X															X								
Urine Pregnancy Test ^r		X			X	X	X			X	X	X	X	X	X			X	X r	X	Xr	X	X	X
Enrollment		X																						
Dispense & Administer VIR- 2218 SC as appropriate (Group A only)		X			X	X	X			X	X													
Dispense & Administer SLGNs as appropriate (Group A only)							X	Х	Х	X	X	X	X	Х										
Dispense & Administer SLGN ^s as appropriate (Group B only)		X	X	X	X	X	X	X	X	X	X													
Study Drug Accountability					X	X	X		X	X	X	X	X	X	X	X								

AE = adverse event; APRI = AST to Platelet Ratio Index; BL = baseline; CT = computed tomography; ddPCR = digital droplet polymerase chain reaction; ECG = electrocardiogram; ED = early discontinuation; EOT = end of treatment; FSH = follicle-stimulating hormone; FU = follow-up; HBcrAg = hepatitis B core-related antigen; HBeAb = hepatitis B e antibody; HBeAg = hepatitis B virus; HBeAb = hepatitis B surface antibody; HBsAg = hepatitis B virus; HCC = hepatocellular carcinoma; HCV = hepatitis C virus; HDV = hepatitis D virus; IV = intravenous; PBMC = peripheral blood mononuclear cells; PK = pharmacokinetic; SAE = serious adverse event; SC = subcutaneous; SLGN = selgantolimod; TAF = tenofovir alafenamide; TSH = thyroid-stimulating hormone

- a All study visits (± 2 days), except for Weeks 1, 2, 13, and 14.
- b FU Week 1 will have a visit window of \pm 2 days, FU Weeks 4 through FU Week 16 will have a visit window of \pm 5 days, and FU Weeks 24 through FU Week 48 will have a visit window of \pm 14 days.
- c Week 1 (Cohort 2 Group B only), Week 13 (Cohort 2 Group A only), and FU Week 1, Week 8, and Week 16 will be conducted as a virtual/telephonic visit to review AEs, concomitant medications, and overall health of the participant by investigator.
- d Week 2 visit is only applicable for Cohort 2 Group B.

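### By-visit HBsAg and HBeAg loss counts participants with no sample due at FU Week 2, and under the printed schedule at FU Week 8, as nonresponders

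*SAP*

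**What the plan says.** **Visits.** Table 3-10 (SAP Section 3.8.2) sets post-treatment windows for HBV DNA, quantitative and qualitative serology, safety laboratories and vital signs in all groups. They include FU Week 2 (FU Days 4 to 22) and FU Week 8 (FU Days 44 to 71). The footnote says that amendment 1 defined FU Week 2 and amendment 2 removed it, and then: "Since a substantial amount of participants have already completed FU Week 2 per protocol amendment 1, this visit will be kept in analysis".

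**Summaries.** Section 6.2.2 performs the secondary analyses on the FAS. For HBsAg: "The proportions of participants with HBsAg loss with and without anti-HBsAg seroconversion will be summarized by cohort and visit". For HBeAg, restricted by baseline status: "The proportion of participants with HBeAg loss with and without anti-HBeAg seroconversion will be summarized by cohort and visit for participants who are HBeAg positive".

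**Missing data.** Section 3.6.1 gives the general rule, "In general, missing data will not be imputed unless methods for handling missing data are specified". Section 6.2.2 then specifies a method for serology: "Missing data will be treated as a nonevent unless otherwise specified (eg, no HBsAg loss, no seroconversion, etc".

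**Schedule.** Appendix Tables 1 and 2 mark follow-up serology and HBV DNA only at FU Weeks 4, 12, 24, 36 and 48. Neither table has an FU Week 2 column. FU Week 8 is remote in both: "Week 13, FU Week 8, and FU Week 16 will be conducted as a virtual/telephonic visit" in Appendix Table 1 (Cohort 1) and "FU Week 1, Week 8, and Week 16 will be conducted as a virtual/telephonic visit" in Appendix Table 2 (Cohort 2).

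**The concern.** Counting a missing result as a failure is a defensible, conservative rule when a sample was due and was not obtained. It has no such justification when no sample was due. The SAP recognises that only part of the study population had FU Week 2, since it gives the number who completed it as its reason for keeping the visit. Yet it sets no matching denominator and leaves the nonevent rule unqualified.

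At stake is the early follow-up part of two named secondary endpoints. A reader of the by-visit table would see a low proportion at FU Week 2 and, possibly, a collapse at FU Week 8 followed by recovery at FU Week 12. That pattern would come from the visit schedule and not from any change in the participants.

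**Working it through.** The SAP gives no planned rate for these endpoints, so there is no figure of its own to reproduce. Two checks were made.

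**1. Which windows can scheduled samples enter?**

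Nominal FU day = 7 × week + 1, which agrees with the FU Day column of Table 3-10. Tolerances come from footnote b of the Appendix 1 tables: ± 5 days for FU Weeks 4 to 16 and ± 14 days for FU Weeks 24 to 48.

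| Sampled visit | Nominal FU day | Range | Table 3-10 window entered |
|---|---|---|---|
| FU Week 4 | 29 | 24–34 | FU Week 4 (23–43) |
| FU Week 12 | 85 | 80–90 | FU Week 12 (72–127) |
| FU Week 24 | 169 | 155–183 | FU Week 24 (128–211) |
| FU Week 36 | 253 | 239–267 | FU Week 36 (212–295) |
| FU Week 48 | 337 | 323–351 | FU Week 48 (296 onward) |

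No scheduled sample falls in Days 4–22 or Days 44–71. If the 5-day early allowance on the end-of-treatment visit shifts the follow-up clock, the FU Week 4 range becomes 19–34. A few early FU Week 4 samples could then enter the FU Week 2 window, but FU Week 8 stays empty. Unscheduled samples, or an early discontinuation visit made during follow-up, could still put isolated results in either window.

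**2. What proportion is displayed?**

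Let p be the true proportion with sustained loss in the FAS and s the share of the FAS with a sample in the window, with sampling assumed independent of response. When unsampled participants are nonevents,

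displayed proportion = p × s.

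The SAP does not give s for FU Week 2, so a range is shown. The planned size of Cohort 1 or of Cohort 2 Group A (n = 40) is used; p is illustrative.

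| s | p = 10% (4/40) | p = 20% (8/40) |
|---|---|---|
| 0% | 0% | 0% |
| 25% | 2.5% | 5% |
| 50% | 5% | 10% |
| 75% | 7.5% | 15% |
| 90% | 9% | 18% |
| 100% | 10% | 20% |

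Take p = 10%, s = 50% at FU Week 2, s = 0 at FU Week 8 and full sampling at FU Weeks 4 and 12. The table would print 5%, 10%, 0%, 10% across FU Weeks 2, 4, 8 and 12, with no participant changing status. Among those sampled at FU Week 2 the proportion is 2/20 = 10%, which is the true value.

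The HBeAg endpoint behaves the same way on a smaller base. The Section 1.2 minimum of 20% HBeAg-positive gives 0.20 × 40 = 8 participants in Cohort 1. A sustained 4/8 = 50% would be displayed as 25% at s = 50%.

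**The case against.** **Amendment 1 is not shown.** Table 3-10 deliberately covers visits from that amendment, so FU Week 8 samples may once have been scheduled. Appendix Table 2 also marks vital signs and a symptom-directed physical examination at FU Week 8 for Cohort 2, despite the telephone footnote, so the row has a use for vital signs. This stands: 0% at FU Week 8 is conditional. Participants followed under the printed schedule would still be miscounted there.

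**The table could be cumulative.** Section 6.2.2 defines HBsAg loss as a change to negative at any visit after baseline, and on a cumulative reading there is no dip. But the same section plans a separate summary of participants who ever had loss, which makes status at each visit the natural reading of the by-visit table.

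**A sample that was never due might not count as missing data.** Section 7.2.2.4 limits by-visit summaries of categorical laboratory data to scheduled visits. Section 6.2.2 contains no such limit, and an intended exception has to be written down.

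**Stronger readings that the document does not support.**

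- A reader might infer that the plan would report false relapses. It would not: Section 6.2.2 defines reversion by an actual positive result, which a missing sample cannot supply.
- A reader might infer that the FU Week 8 ALT values plotted under Section 7.2.1 would come mainly from participants with flares. Nothing says why off-schedule samples would be drawn, the nonevent rule does not touch ALT, and n is reported at each visit.
- A reader might infer a bias between Groups A and B, because Group B treatment was discontinued early. The SAP gives no FU Week 2 counts by group, so neither the existence nor the direction of a difference can be established.

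**Conclusion.** The point holds for the by-visit HBsAg and HBeAg displays. As written, Section 6.2.2 and Table 3-10 together count participants with no sample due as having no loss. At FU Week 2 the displayed proportion is about p × s; only the fact that s is below 1 for some participants follows from the footnote, and its value is unknown. At FU Week 8 the displayed proportion tends to 0% if amendment 1 scheduled no sample there.

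The result rests on three assumptions: the table shows status at each visit, sampling is unrelated to response, and there are responders at those visits. The reach is limited to descriptive secondary displays in a study with no formal testing. The FU Week 24 primary endpoint and the summaries of participants who ever had loss do not depend on these two windows in this way. It should be corrected because the rule as stated gives a wrong proportion and the correction is simple.

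**What to change.** - In Section 6.2.2, state that missing counts as nonevent only at visits where the sample was scheduled under the protocol amendment in force for that participant.
- At FU Week 2, use participants with a sample in the window as the denominator and show n. Do the same at FU Week 8 if amendment 1 scheduled samples there.
- If it did not, omit FU Week 8 from the by-visit serology, HBV DNA and laboratory displays and list any off-schedule results. The row can remain in Table 3-10 for vital signs.
- Do not reassign FU Days 44 to 71 to FU Week 4 or FU Week 12. Section 3.8.3 selects the most favourable serology result and the largest ALT in a window, so an off-schedule sample could displace the scheduled value at a well-sampled visit.

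The cost is an edit to Section 6.2.2, a note to Table 3-10 and a denominator change in programming. The small downside is that FU Week 2 then rests on a subset, which the displayed n makes plain.

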3.8.2. Analysis Visit Windows

Participant visits might not occur on protocol-specified days. Therefore, for the purpose of analysis, observations will be assigned to analysis windows as specified in Table 3-1 to Table 3-12.

Data collected up to the last on-treatment date + 3 days will be considered as on-treatment data, whereas data collected afterwards will be considered as follow-up data.

For each drug, the last on-treatment date is defined as follows:

- Last on-treatment date for VIR-2218 = (last injection date of VIR-2218 + 28 days) -1
- Last on-treatment date for nivolumab = (last injection date of nivolumab + 28 days) 1
- Last on-treatment date for selgantolimod = (last dose date of selgantolimod + 7 days) -1

For Cohort 1 and Cohort 2 Group A, the composite last on-treatment date is the latest date of the last on-treatment date of VIR-2218, nivolumab, or SLGN.

For Cohort 2 Group B, the composite last on-treatment date is the latest date of the last on-treatment date of nivolumab or SLGN.

Participants are allowed to continue taking TAF after the discontinuation of study treatments, hence TAF will not be considered for constructing the analysis windows.

The follow-up day (FU Day) in Posttreatment tables is defined as:

• FU Day = Assessment date – composite last on-treatment date.

A baseline value is defined as the last available value collected on or prior to the date of first dose of any study drug. An unscheduled visit prior to the first dosing of study drug will be included in the calculation of the baseline value, if applicable.

The analysis windows for on-treatment assessments are provided in Table 3-1 to Table 3-9. Table 3-10 to Table 3-12 provide analysis windows for posttreatment assessments.

Table 3-1. Cohort 1 and Cohort 2 Group A: Analysis Visit Windows for On-treatment Vital Signs, Hematology, Chemistry, Coagulation, Quantitative Plasma HBV DNA, Quantitative HBV (serum HBsAg, HBcrAg, HBeAg, and HBV RNA), Qualitative HBV Serology (HBeAg, hepatitis B e antibody (HBeAb), HBsAg, and hepatitis B surface antibody (HBsAb))

		Visit Window Study Day	
Visit	Study Day	Lower Limit	Upper Limit
Baseline	1	(none)	1
Week 4	29	2	43
Week 8	57	44	71
Week 12	85	72	92
Week 14	99	93	106
Week 16	113	107	127
Week 20	141	128	155
Week 24	169	156	183
Week 28	197	184	211
Week 32	225	212	239
Week 36	253	240	≥ 253

Table 3-2. Cohort 1 and Cohort 2 Group A: Analysis Visit Windows for On-treatment Urinalysis

		Visit Windo	w Study Day

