7.5. Electrocardiogram Results

Electrocardiogram (ECG) analysis results are intended to identify meaningful abnormalities. If potential abnormalities of interest are identified, further analyses may be conducted.

A shift table of the investigators' assessment of ECG results at Weeks 12 and 36 for Cohort 1 and Cohort 2 Group A, or Weeks 12 and 24 for Cohort 2 Group B compared with baseline values will be presented by cohort (and by treatment group for Cohort 2) using the following categories: normal; abnormal, not clinically significant; abnormal, clinically significant; or missing. The number and percentage of participants in each cross-classification group of the shift table will be presented. Participants with a missing value at baseline or postbaseline will not be included in the denominator for percentage calculation. No formal statistical testing is planned.

A by-participant listing for ECG assessment results will be provided by participant ID number and visit in chronological order.

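### Table 3-12 labels any posttreatment body weight or creatinine clearance from FU Day 4 onward as FU Week 48, and a late EOT or early-discontinuation ECG has no place in the shift table

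*SAP*

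**What the plan says.** Section 3.8.2 separates treatment from follow-up by date: "Data collected up to the last on-treatment date + 3 days will be considered as on-treatment data", and later data are follow-up. The follow-up clock is "FU Day = Assessment date – composite last on-treatment date". The composite date is the latest of the drug-specific dates. For the weekly tablet the rule is "Last on-treatment date for selgantolimod = (last dose date of selgantolimod + 7 days) -1"; for VIR-2218 and nivolumab it is the last injection plus 27 days.

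The last of the window tables, "Table 3-12. Cohort 1, Cohort 2 Groups A and B: Analysis Visit Windows for Posttreatment Body Weight, ECG, Estimated Creatinine Clearance", has a single row: "FU Week 48 337 4 ≥ 337". Table 3-10, which covers chemistry, vital signs and HBV markers, has seven follow-up rows and starts FU Week 48 at FU Day 296.

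Appendix 1 schedules body weight, ECG and creatinine clearance at EOT, at the ED visit and at FU Week 48. The Cohort 1 footnote on the ED visit adds: "If ED is done in FU period, all of these procedures should be performed".

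Sections 7.2.1 and 7.3 summarize eGFR and body weight at every postbaseline visit. Section 7.5 plans "A shift table of the investigators' assessment of ECG results at Weeks 12 and 36 for Cohort 1 and Cohort 2 Group A" (Weeks 12 and 24 for Group B), with no posttreatment column.

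**The concern.** A window that opens at FU Day 4 is harmless only if nothing but the FU Week 48 visit can fall inside it. Here an EOT or ED visit can, and the SAP has no EOT or ED analysis row to receive it.

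Two things follow. Weight and eGFR taken shortly after treatment can be presented as 48-week follow-up data. An ECG meant as the end-of-treatment reading can drop out of the only planned ECG table. The participants most exposed are those whose dosing or participation ended early, and their end-of-treatment safety readings matter particularly.

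**Working it through.** **Reproducing the SAP's own limits.** Nominal FU Week 48 = 48 × 7 + 1 = 337. Adjacent windows are split at the midpoint:
- Table 3-10: (253 + 337)/2 = 295, so FU Week 48 starts at 296.
- Table 3-11: (85 + 337)/2 = 211, so it starts at 212.
- Table 3-12: there is no neighbouring visit, so the lower limit falls to the end of the on-treatment allowance, 3 + 1 = 4.

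The row is therefore the SAP's window convention applied to a single scheduled visit.

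**Width.** The earliest accepted value is 337 − 4 = 333 days before nominal. Appendix 1 allows ±14 days for this visit, that is FU Days 323 to 351.

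**EOT visit, Cohort 1 and Cohort 2 Group A.** SLGN starts at Week 12 (Day 85) and is given weekly for 24 doses. The EOT visit is planned for Day 253 with a window of −5 days, so Days 248 to 253.

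| Step | All 24 doses | Final dose missed |
|---|---|---|
| Last SLGN dose | 85 + 23 × 7 = Day 246 | 85 + 22 × 7 = Day 239 |
| Last on-treatment date (+6) | Day 252 | Day 245 |
| On-treatment through (+3) | Day 255 | Day 248 |
| EOT on Day 253 is FU Day | 1 | 8 |
| Table 3-12 or on-treatment label | Week 36 | FU Week 48 |

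VIR-2218 does not move the second column: its last scheduled injection is at Week 20 (Day 141), and 141 + 27 = Day 168. A nivolumab infusion at Week 32 would: 225 + 27 = Day 252 restores the first column. With the final SLGN dose missed and no such infusion, Days 249 to 253 (5 of the 6 permitted EOT days) count as follow-up. After full dosing, only an EOT on Day 256 or later, three or more days late, crosses over.

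**ED visit during follow-up.** At FU Weeks 4, 12, 24 and 36 (FU Days 29, 85, 169 and 253), Table 3-12 assigns FU Week 48, which is 308, 252, 168 and 84 days before nominal.

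**One visit, two labels.** Take an ED visit on FU Day 20. Under Table 3-10 its serum creatinine and vital signs belong to FU Week 2 (FU Days 4 to 22). Under Table 3-12 its body weight and the Cockcroft-Gault value belong to FU Week 48, although Section 5.2 calculates Cockcroft-Gault from creatinine and weight. The labels differ by 48 − 2 = 46 weeks.

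**What the tables then show.** For continuous values, Section 3.8.3 keeps the record closest to the nominal day.
- If a true FU Week 48 value exists, it is selected, and the earlier value leaves the by-visit summary.
- If none exists, the earlier value is reported as FU Week 48. Section 1 applies this SAP to the Primary Analysis at FU Week 24, when a participant may not yet have reached FU Week 48.

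For ECG, the Week 36 window in Table 3-4 starts at Day 170, and the EOT (or ED) ECG is the only one scheduled in it. If that reading is classed as follow-up, the participant has no Week 36 value. Section 7.5 then removes the participant from the denominator.

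**The case against.** The case for leaving the table alone has several sound parts:
- An on-time EOT visit after full dosing maps to Week 36, and the 3-day allowance absorbs small slippage.
- FU Day 4 is not 4 days after the last dose. It is 10 days after the last SLGN dose, or 31 days after an injection when that sets the composite date.
- The requirement to perform the full ED panel in follow-up is written only in the Cohort 1 schedule; the Cohort 2 footnote lacks it.
- The wide window follows the SAP's general practice. Table 3-11, for example, opens FU Week 12 at FU Day 4.
- FU Day 296 is the midpoint with FU Week 36, a visit at which these three assessments are not scheduled.

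Three stronger readings might be inferred, and the SAP supports none of them.
- **Early ECGs are tabulated as one-year data.** No planned table has a FU Week 48 ECG column, and all ECGs stay in the listing.
- **EOT renal and other safety information is lost.** Treatment-emergent adverse events and laboratory abnormalities are defined by date, through the composite date plus 30 days (Sections 7.1.6.1 and 7.2.2.1). A creatinine on FU Day 8 therefore still counts.
- **FU Week 48 summaries are contaminated for completers.** The closest-to-nominal rule selects their true value.

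These points narrow the reach but do not justify the row. The convention explains how FU Day 4 arose. It does not make a value 333 days early a FU Week 48 value, nor reconcile it with the Table 3-10 label for the same visit.

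**Conclusion.** The point holds as a labelling defect in the by-visit body weight and eGFR summaries, with a related gap in the ECG shift table.

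It affects participants who have an EOT or ED value on FU Day 4 or later. The mislabelling of weight and eGFR further requires that they have no true FU Week 48 value at the time of analysis. A reported value can be up to 333 days from nominal.

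The missed-final-dose example assumes that no Week 32 nivolumab infusion was given. The SAP gives no count of missed doses, late EOT visits or ED visits in follow-up, so the number affected cannot be computed. The primary endpoint uses Table 3-10 and is untouched.

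**What to change.** 1. In Table 3-12, set the lower limit of FU Week 48 to FU Day 296, as in Table 3-10.
2. Add a separate posttreatment (EOT/ED) row for FU Days 4 to 295 to the body weight and eGFR summaries. This row has no nominal day, so state which record is used when there is more than one.
3. Add the same row to the Section 7.5 ECG shift table. The worst-value rule in Section 3.8.3 already settles multiple ECGs.
4. Leave the on-treatment plus 3 days rule as it is. Moving later EOT values back into Week 36 would override that rule and label follow-up data as on-treatment.

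The cost is a table edit and a small programming change. Fewer participants will have a FU Week 48 weight or eGFR, but those shown will come from near that visit.
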